Rationnel et Objectifs	
Le cytochrome P450 2C19 (CYP2C19) est l'enzyme responsable du métabolisme de médicaments fréquemment prescrits en clinique comme l'oméprazole, un antiacide inhibiteur de la pompe à proton (IPP), le citalopram, un antidépresseur inhibiteur sélectif de la recapture de la sérotonine (ISRS) ou le clopidogrel, un antiagrégant plaquettaire. Le CYP2C19 présente une importante variabilité interindividuelle de son activité dans la population générale due, notamment, à un fort polymorphisme génétique, avec une trentaine de variants alléliques identifiés à ce jour. Ceci résulte en cinq phénotypes distincts dans son activité : le phénotype métaboliseur lent (PM), le phénotype métaboliseur intermédiaire (IM), le phénotype métaboliseur normal (NM), le phénotype métaboliseur rapide (RM) et le phénotype métaboliseur ultra-rapide (UM).
 
Pour caractériser l'activité du CYP2C19, il existe différentes méthodes de phénotypage à savoir l'administration d'une substance-test métabolisée de manière spécifique par le CYP2C19 et la mesure de paramètres pharmacocinétiques, tels que l'aire sous la courbe (AUC), ou des ratios métaboliques entre les concentrations de la molécule-mère et de son métabolite. Les substances-tests les plus utilisées sont l'oméprazole (OPZ) et la méthénytoïne. Il est également possible de mesurer le phénotype de plusieurs isoformes des CYPs simultanément avec le phénotypage mixte, tel que le « Geneva cocktail » développé aux HUG. Ce dernier est composé de 6 substances-tests permettant de phénotyper simultanément 6 isoformes des CYPs, dont l'OPZ pour le CYP2C19.
 
Malgré une bonne tolérance de ce cocktail, certains patients peuvent être réticents à l'administration de médicaments de manière exogène et il n'est parfois pas possible de les administrer à certains patients (e.g. femmes enceintes, enfants, personnes âgées). Il convient par ailleurs d'attendre 2h après l'ingestion du « Geneva cocktail » avant d'effectuer la prise de sang, ce qui peut poser quelques contraintes pratiques en clinique.
 
L'utilisation de biomarqueurs endogènes de mesure de l'activité des CYPs permettrait ainsi de s'affranchir de ces obstacles et de rendre la pratique moins invasive et plus acceptable pour les patients. Une récente étude consacrée au CYP2D6 conduite au sein de notre service a permis d'identifier de nouveaux biomarqueurs endogènes pour cet isoforme, à savoir la solanidine, un alcaloïde aglycone très commun, et ses dérivés.
 
Le but de notre étude est d'identifier de nouveaux biomarqueurs endogènes pour mesurer (phénotyper) l'activité du CYP2C19 par métabolomique non ciblée.
 
Les volontaires sains seront stratifiés en deux groupes selon leur phénotype pour le CYP2C19 : les sujets PMs et NM-RMs-UMs. Les sujets IMs seront exclus afin d'observer des différences plus significatives au sein des deux groupes.
 
Objectif primaire :
 
 - Partie 1 : mise en évidence de potentiels substrats et/ou métabolites endogènes du CYP2C19 par métabolomique non ciblée sur des échantillons urinaires, plasmatiques et de vésicules extracellulaires dérivées du foie prélevés avant (baseline, session 1) et après administration répétée de fluvoxamine (inhibition enzymatique du CYP2C19, session 2) ainsi qu'après administration répétée de rifampicine (induction enzymatique du CYP2C19, session 3). - Partie 2 : identification des substrats et/ou métabolites endogènes du CYP2C19 parmi les composés mis en évidence dans la partie 1 par analyse semi-quantitative ciblée sur des échantillons urinaires, plasmatiques et de vésicules extracellulaires dérivées du foie des volontaires sains PMs et NM-RMs-UMs à la baseline (i.e sans administration préalable de fluvoxamine ou de rifampicine). 
Objectifs secondaires :
 
 - Identification des substrats et/ou des métabolites endogènes du CYP2C19 à l'aide de bases de données internes ou externes, par fragmentation en LC-MS/MS ou à l'aide de standards de référence. - Corrélation des concentrations plasmatiques et/ou urinaires et/ou de vésicules extracellulaires dérivées du foie d'un substrat et/ou un métabolite endogène du CYP2C19 avec le phénotype (ratio sanguin OH-oméprazole/oméprazole) et/ou le génotype du CYP2C19.

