Méthode	
Le projet consiste en trois parties expérimentales :
 
 - Partie 1 : mesure de l'impact d'un inhibiteur du CYP2C19, la fluvoxamine, sur le métabolome urinaire, plasmatique et de vésicules extracellulaires dérivées du foie - Partie 2 : mesure de l'impact d'un inducteur du CYP2C19, la rifampicine, sur le métabolome urinaire, plasmatique et de vésicules extracellulaires dérivées du foie - Partie 3 : mise en évidence des biomarqueurs du CYP2C19 par mesure de l'impact des polymorphismes du CYP2C19 sur les composés affectés dans les parties 1 et 2. 
Il s'agit d'une étude ouverte à design croisé chez des volontaires sains répartis en deux groupes selon leur génotype du CYP2C19 (PMs et NMs-RMs-UMs). Trois sessions auront lieu pour chaque sujet :
 
Session 1 : prélèvements plasmatique et urinaire ainsi que la détermination du ratio sanguin OH-oméprazole/oméprazole à la baseline par prise de sang capillaire.
 
Session 2 : idem session 1 avec prise au préalable de 50 mg de fluvoxamine pendant 7 jours consécutifs (inhibiteur fort du CYP2C19).
 
Session 3 : idem session 1 avec prise au préalable de 600 mg de rifampicine pendant 10 jours consécutifs (inducteur fort du CYP2C19).
 
A chaque session, une récolte urinaire sur 24h est effectuée, suivie d'une prise de sang veineux (6 x 6 ml) le matin à jeun. Le phénotypage a ensuite lieu avec la prise d'oméprazole à 10 mg, suivie d'une prise de sang capillaire (4 x 10 µl) après 2h. Après la session 1, la prise de fluvoxamine a lieu durant 7 jours consécutifs (administration au total de 7 doses de fluvoxamine à 50 mg), pouvant commencer au moment du repas de midi lors du déroulement de la session 1. La dernière prise de fluvoxamine doit avoir lieu 2h avant l'administration d'oméprazole à 10 mg lors de la troisième visite (jour 11±4j, session 2). Enfin, la prise de rifampicine aura lieu au moins 6 jours après la session 2, tous les soirs durant 10 jours consécutifs (administration au total de 10 doses de rifampicine à 600 mg). La dernière prise de rifampicine doit avoir lieu le soir de la veille de l'administration d'oméprazole à 10 mg lors de la quatrième visite (jour 27±4j, session 3).

Nombre de volontaires	40 volontaires sains : 10 PMs et 30 NMs-RMs-UMs
Durée de l'étude	Au minimum 24 jours et au maximum 32 jours par volontaire

[figure not shown]

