3. STUDY DESIGN

3.1 Overall description

The study will be an open-label study with a total of 40 healthy volunteers fulfilling inclusion/non-inclusion criteria, divided into 2 study groups: 10 healthy volunteers PMs and 30 NMs-RMs-UMs for CYP2C19 and participating in the three sessions:

- Session 1: urine and venous blood sampling. Determination of blood $MR_{OH-OPZ/OPZ}$ at baseline (no inhibitor administrated).
- Session 2: urine and venous blood sampling. Determination of blood $MR_{OH-OPZ/OPZ}$ after pre-treatment by fluvoxamine (strong inhibitor of CYP2C19).

- Session 3: urine and venous blood sampling. Determination of blood MR_{OH-OPZ/OPZ} after pre-treatment by rifampicin (strong inducer of CYP2C19).

Information:

At this step, the volunteer will have an interview with one of the co-investigators at the Clinical Pharmacology and Toxicology department and the study will be explained in detail. A sufficient time will be allowed before the inclusion session to guarantee sufficient time for reflection.

Inclusion:

Volunteers willing to participate and having signed the informed consent form (ICF) will undergo a clinical evaluation with a physician including liver and kidney tests, body mass index, genotyping (except if CYP2C19 genotype is already known) and a pregnancy test (women only). Women will be asked to use at least one physical contraceptive barrier (i.e. male or female condom, diaphragm, spermicide) throughout their study participation and 1 month after the end of the study, in addition of their hormonal contraception if applicable. In case of heavy menstrual bleeding, women will have to be recruited before or after their menstrual period to avoid the presence of blood in urine. In addition, all volunteers will be asked to avoid alcohol consumption on days of taking study drugs and 48 hours before day 0 of session 1. A volunteer code for the study will be assigned to each volunteer included in the study.

Only volunteers fulfilling the inclusion/non-inclusion criteria will be allocated to a study group.

Sessions course:

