3.2 Primary and secondary endpoints

Primary endpoint:

Fold-change in the intensities of features determined by mass spectrometry according to genotype (PMs versus NMs-RMs-UMs) and according to sessions. Metabolic features showing a fold-change ≥ 1.5 or ≤ 0.67 ³⁷ will be qualified as CYP2C19 endogenous biomarkers. Chromatographic signals will be detected in healthy volunteers' urine, plasma and liver-derived

extracellular vesicles by liquid chromatography coupled to high resolution mass spectrometry (LC-HRMS) at each session for each volunteer.

Secondary endpoint:

- Correlation of significant ions measured in metabolomics with OH-OPZ/OPZ blood ratio.
- Establishment of a multivariate linear regression model to predict CYP2C19 phenotype.

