4. STUDY POPULATION

4.1 Selection and recruitment procedures

Volunteers will be recruited through advertisements approved by the “commission cantonale d’éthique et de la recherche” (CCER) of Geneva and displayed in different public buildings or

transmitted by email and social media. After a first contact (either telephonic or by e-mail), potential volunteers will be invited to participate to an information session at which the study aim and design as well as possible risks will be explained. After allowing at least 72 hours for reflection, volunteers willing to participate in the study will sign the consent form. In the next step, they will be subject to a screening procedure including a review of volunteer's medical history and current health status, physical examination, hepatic and renal tests, body mass index determination, pregnancy test (for women) and genetic testing for CYP2C19.

After evaluation of the inclusion and non-inclusion criteria, eligible volunteers will be allocated to a study group (CYP2C19 PMs or NMs-RMs-UMs) and will attend sessions 1, 2 and 3.

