9. STATISTICS

9.1 Number of subjects

The data from Bosilkovska et al.²⁴, Magliocco et al.³⁷, Zhou et al.¹¹ and Akasaka et al.⁴⁰ were used as a basis to measure the effect size required for our clinical study and the number of subjects required for each study group.

The software G*Power (version 3.1.9.7) was used to calculate the sample size for a two-sided paired samples t-test with a power ($1-\beta$) of 80% for the part 1 of the study. The Bonferroni correction was applied to adjust the p-value (α = type 1 error) in order to correct for multiple tests as it is the case in metabolomics analyses. Therefore, p-value is divided by the number of expected features, which was defined as 5000 according to the number of metabolic features obtained after data processing in the Magliocco et al. clinical study, of which metabolomics were used to prospect on CYP2D6 endogenous biomarkers³⁷. Consequently, the p-value used for the power calculation will then be $1 \cdot 10^{-5}$. Moreover, the effect size obtained for the statistical analysis and based on the Bosilkovska et al. trial is 1.156. After entering all these parameters, a sample size of 30 is measured, which implies that 30 healthy volunteers NMs-RMs-UMs are required to observe a difference between control session, inhibition session and induction session in the part 1 of the study.

For the second part of the study (validation of identified features in the first part), a semi-quantitative targeted analysis will be performed. In Zhou et al.¹¹ study, 14% of the total number of participants were PM individuals among all the study participants and were enrolled to confirm a statistical difference between CYP2C19 PMs and non-PMs in the pharmacokinetic of a single 20 mg dose of omeprazole. Moreover, 35% of the total number of patients were PMs in the study of Akasaka et al.⁴⁰ where PMs and non-PMs were compared to have a significant difference between serum EETs levels (potential endogenous biomarker of CYP2C19).

Following these data, 10 PM individuals i.e. 10 subjects, which is 25% of the total number of our subjects (mean proportion of Zhou et al. and Akasaka et al. studies when combined), will be recruited. Therefore, already genotyped healthy volunteers known from our database or new ones will be contacted and if achievable, 10 PMs and 30 NMs-RMs-UMs (40 in total) subjects will be recruited and compared to each other at baseline.

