9.2 Data analysis

For metabolomics analysis, peak extraction and grouping as well as retention time correction and alignment will be performed on XCMS Online.⁸³ Then, multivariate statistical analysis as

well as univariate will be done. First of all, regarding multivariate approaches, a principal component analysis will be applied to verify the analytical variability. Partial least squares-discriminant analysis (PLS-DA), the supervised version of PCA, will also be used to maximise the separation between different groups (i.e. control session versus inhibition session versus induction session). Then, the variable importance in projection (VIP) score calculated from the PLS-DA model may be applied to identify potential biomarkers.

In univariate analysis, a volcano plot will be performed to detect any significant changes in signal intensities before and after inhibition or induction as well as between PMs and NMs-RMs-UMs. The raw p-values will be adjusted by false discovery rate method to correct for multiple testing in the first case.

All the metabolomics analysis will be performed on the online platform Metaboanalyst.⁸⁴

The possible correlation between the blood MR OH-OPZ/OPZ and significant ions identified will be evaluated using Spearman's rank correlation. Values of $p < 0.05$ will be considered significant.

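### Poor metabolisers take both drugs, but no stated analysis compares their change from session 1 with that of the other group; separately, section 3.1 is wrong that paired samples leave no bias.

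*Protocol*

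**What the plan says.** **Who takes the drugs.** Section 3.1 enrols "10 healthy volunteers PMs and 30 NMs-RMs-UMs for CYP2C19 and participating in the three sessions". Section 4.1 says that eligible volunteers are "allocated to a study group (CYP2C19 PMs or NMs-RMs-UMs) and will attend sessions 1, 2 and 3". So the 10 PMs receive fluvoxamine before session 2 and rifampicin before session 3, like everyone else.

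**Where the genotype comparison sits.** Section 9.1: "10 PMs and 30 NMs-RMs-UMs (40 in total) subjects will be recruited and compared to each other at baseline". The synopsis objectives (Partie 2) agree, comparing "volontaires sains PMs et NM-RMs-UMs à la baseline (i.e sans administration préalable de fluvoxamine ou de rifampicine". The other places give no session:
- Synopsis, Méthode, Partie 3: the impact of "polymorphismes du CYP2C19 sur les composés affectés dans les parties 1 et 2".
- Section 3.2, primary endpoint: fold-change "according to genotype (PMs versus NMs-RMs-UMs) and according to sessions".
- Section 9.2, volcano plot: "to detect any significant changes in signal intensities before and after inhibition or induction as well as between PMs and NMs-RMs-UMs".

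The PLS-DA groups in section 9.2 are the three sessions; genotype is not a factor.

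**What the drugs do.** Section 5.1.2 describes fluvoxamine as a potent inhibitor of CYP1A2 as well as CYP2C19, and a moderate inhibitor of CYP2C9, 2D6 and 3A4. Section 5.1.3 describes rifampicin as a strong inducer of CYP2C8, 2C9 and 3A4/5 as well as 2C19. Section 4.4 defines PMs as carriers of two non-functional alleles.

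**Session order.** Section 3.1 says that the order is deliberately not randomised, on the ground that a PK study on paired samples has no bias for randomisation to address.

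**The concern.** The trial asks whether a metabolic feature reflects CYP2C19. A before/after change under fluvoxamine or rifampicin does not settle that, because the protocol itself lists other isoforms that each drug affects. PMs have no functional CYP2C19 allele. A drug response of the same size in PMs and in NM-RM-UMs therefore argues for another pathway, for a time effect, or for both. The design collects the samples that would show this, but no stated analysis sets the two groups' drug responses against each other.

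The reason given in section 3.1 for the fixed order bears on the same inference. Pairing removes differences between subjects. It does not remove whatever else changes between day 1 and session 2 or 3. With one order for everyone, drug and time cannot be separated within subjects. Effects of time and off-target drug effects cancel in a PM versus NM-RM-UM comparison of change, provided the two groups share them.

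**Working it through.** **1. The plan's own figure.** Section 9.1 uses a two-sided paired t-test, effect size 1.156, alpha 0.05/5000 = 1e-5 and power 80%. The noncentrality is 1.156 × √n. Exact noncentral-t power is 76.8% at n = 29 and 80.4% at n = 30. The stated 30 reproduces and is not disputed.

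**2. What enters a between-genotype comparison.** There are 40 × 3 = 120 subject-sessions. If the genotype comparison is at baseline only, 10 × 2 = 20 of them (PMs in sessions 2 and 3) enter no between-genotype comparison. They may still enter the omeprazole-ratio correlation and the cell-free RNA analyses.

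**3. Precision of the missing contrast.** Take the change from session 1 in log intensity, NM-RM-UM (30) minus PM (10), in units of the SD of change, equal SDs, df = 38.
- SE = √(1/30 + 1/10) = 0.365 SD.
- 95% CI half-width = t(0.975, 38) × 0.365 = 2.024 × 0.365 = 0.74 SD.
- Without pooling (Welch), the half-width is 0.78 SD at equal SDs and 1.11 SD if the PM SD is 1.5 times larger.

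**4. Power, under a borrowed effect.** The protocol gives no between-genotype effect for change. As an assumption, NM-RM-UMs change by its within-subject value of 1.156 SD, and PMs by 0, 0.3 or 0.5 SD. The difference d is then 1.156, 0.856 or 0.656, and the noncentrality d/0.365 is 3.17, 2.34 or 1.80. The threshold 0.05/50 = 0.001 assumes a shortlist of 50 features.

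| PM change (SD) | Expected 95% CI (SD) | Power at 0.05 | Power at 0.05/50 |
|---|---|---|---|
| 0 | 0.42 to 1.90 | 87% | 36% |
| 0.3 | 0.12 to 1.60 | 63% | 13% |
| 0.5 | -0.08 to 1.40 | 42% | 5% |

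**5. Use as a ranking.** Suppose an off-target feature changes by 1.156 SD in both groups, so its expected contrast is 0, and that features are independent with equal SDs.
- Against one such feature, a true feature ranks higher with probability Φ(d/(0.365 × √2)) = 99%, 95% or 90% for PM changes of 0, 0.3 and 0.5 SD.
- A shortlist holds many features. The chance of outranking all of 50 is the integral of φ(x) × Φ(x + d/0.365)^50 over x, which is 80%, 54% or 34%.

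The second line is the fairer guide to what the contrast can do.

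**The case against.** The strongest reply is that this is an extra analysis, not an error. The plan screens within subjects and then tests genotype at baseline. It adds a correlation ("The possible correlation between the blood MR OH-OPZ/OPZ and significant ions identified will be evaluated") and, under section 2.9, validation with recombinant enzymes and genotyped hepatocytes. A supportive ranking could be left to a statistical analysis plan. Most of this stands: the contrast adds to a plan that already has specificity checks. It is still worth raising, because the protocol gives both drugs to all PMs and names a genotype comparison only at baseline.

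A second reply concerns the fixed order. An inhibitor and an inducer should move a CYP2C19 feature in opposite directions, which a steady time trend would not mimic. That is a real strength of the design, although the protocol states no rule requiring opposite changes. The order may also be well founded, since section 5.1.3 says that induction lasts for two weeks after rifampicin stops. Section 3.1 does not give that reason. The reason it does give is incorrect, and the reply does not rescue that sentence.

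Three stronger readings are tempting, and the documents do not support them:
- A reader might infer that sections 3.2 and 9.2 contradict the baseline plan. They are silent on the session, which is not a conflict.
- A reader might infer that the before/after screen is confined to the 30 NM-RM-UMs. Section 9.1 only sizes it on them, and no passage restricts the analysis in section 9.2 to that group.
- A reader might infer that the PMs' drug-session data are unused. The omeprazole ratio is measured at all three sessions and section 9.2 does not limit the correlation to baseline. The cell-free RNA objective draws on genotype and modulation.

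**Conclusion.** Two points hold. First, no passage compares change from session 1 between PMs and NM-RM-UMs, although all PMs take both drugs and the protocol describes both drugs as acting on other CYPs. Adding that contrast is a cheap gain in in vivo specificity. With 10 PMs it is imprecise: the half-width is about 0.74 SD. Power is 87% at 0.05 and 36% at 0.05/50 in the favourable case where PMs do not change. These figures rest on the borrowed 1.156 and equal SDs of change. The ranking figures also assume independent features and off-target responses that are equal in both genotypes. The protocol gives none of these for this contrast, so the figures illustrate scale and do not predict.

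Second, the statement in section 3.1 that pairing removes any bias needing randomisation is wrong as written. This does not show that the fixed order is the wrong choice, nor that any result is biased. It shows that the stated reason does not support it.

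**What to change.** **Section 9.2.** For features shortlisted from the inhibition and induction sessions, report the difference in change from session 1 (NM-RM-UM minus PM, log intensity), separately for sessions 2 and 3, each with its 95% CI. Label it supportive evidence, not a filter.

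**Section 3.1.** Replace the sentence on randomisation with three statements: the order is fixed, the reason for it, and that drug is confounded with time. Add that the PM group controls for time and off-target drug effects together, not for time alone.

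**Optional.** Name baseline as the session of the genotype comparison in sections 3.2 and 9.2, to match section 9.1 and the synopsis objectives.

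**Cost.** Wording only, with no new samples or visits. The downside is the imprecision shown above. In addition, a CYP2C19 feature also handled by CYP2C8 or 2C9, as section 2.6 says of arachidonic acid, may change in PMs too. Its contrast then shrinks and it would be ranked too low, which is why the contrast should not exclude features.

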2.2 Cytochromes P450

Cytochromes P450 (CYP450) constitute the main enzyme family responsible for oxidative metabolism (phase I) of major drugs and xenobiotics.³ In human, 57 functional genes have been identified. These are grouped in 18 families and 44 sub-families.⁴ Most of them have endogenous functions such as biosynthesis of steroid hormones, prostaglandins and bile acids.⁵ Drugs are metabolized by only 12 CYP isoenzymes, which belong to families 1-3. The most important isoenzymes in drug metabolism are CYP3A4/5 (which metabolizes 30.2% of drugs), CYP2D6 (20%), CYP2C9 (12.8%), CYP1A2 (8.9%), CYP2B6 (7.2%), and CYP2C19 (6.8%).⁶

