CYP2C19 is also subject to variability due to environmental, physiological and pathological factors. Inhibition by many drugs has been reported (such as with fluvoxamine)^{15,16}, as well as induction (such as with rifampicin)¹⁷. Finally, CYP2C19 activity might also be influenced by pregnancy, oral contraceptives and gender.¹⁸⁻²⁰

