4.4 Assignment to study groups

Each eligible participant will be assigned to a study group according to his CYP2C19 genotype. The first group will be composed of carriers of two non-functional alleles of CYP2C19 (PMs). The second group will be composed of carriers of two normally functional alleles (NMs), one normally functional allele and one increased-functional allele (RMs) or two increased-functional alleles of CYP2C19 (UMs).

IM subjects will not be included in the clinical study because of the intermediate activity of the enzyme that may not highlight significant changes in the metabolome when compared to the metabolome of PMs or NMs. In addition, NMs, RMs and UMs are grouped together because of the potentially low changes in the metabolome between them as it has been found for the endogenous DHETs blood levels and many exogenous compounds such as omeprazole, pantoprazole and lansoprazole.^{8,10,11,40,51}

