Rifampicin acts as a strong inducer of CYP2C8, 2C9, 2C19 as well as 3A4/5 and a weak inducer of CYP1A2 and 2B6.^{17,24,50,64,70,71} Consequently, many concomitantly administered classes of drugs such as benzodiazepines, calcium antagonists, protease inhibitors and neuroleptics become ineffective. This also includes oral contraceptives, which makes barrier contraceptive method an important requirement. Furthermore, induction does not dissipate until 2 weeks after discontinuing rifampicin, reinforcing the need to use a barrier contraceptive method after stopping treatment (i.e. male or female condom, spermicide or diaphragm).^{64,70,72} In this study, at least one barrier contraceptive method will have to be used for all the study duration and for 1 month after the last visit (session 3). During this period, women who usually take oral contraceptives can keep their intake while using a barrier contraceptive method. It is necessary to administer rifampicin for at least 7 days to achieve the onset of full enzymatic induction. Therefore, 10 days will be applied here, which is sufficient to increase the concentration of endogenous CYP2C19 metabolites.⁷²

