8. QUALITY CONTROL AND ASSURANCE

8.1 Data handling and record keeping/archiving

8.1.1 eCRF

The electronic Case Report Form (eCRF) is an investigator file, written for each study subject, which contains data necessary to the progress and the analysis of the study, including safety data.

In this study, the following data will be entered in the eCRF using the browser-based software REDcap :

- Review of inclusion and non-inclusion criteria (check boxes) *
- Demography: gender*, age*
- Concomitant medication(s)*
- weight*, size* and BMI*
- CYP2C19 genotype and phenotype
- For women: date of last menstrual cycle, contraception methods and pregnancy test result at each visit*
- Time of drug intakes*
- Time of venous and capillary blood samplings*
- Time of urine collections*
- SAE resulting in death and SUSARs*

All items followed by an asterisk will be entered directly in the eCRF and will be considered source documents.

Each page will include the subject's and visit's number as well as all the modifications dated and signed by the investigator.

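### The baseline comparison of 10 PMs with 30 NM-RM-UMs takes no account of sex, so sex-dependent ions can lose a material part of their power and cross the fold-change limits more often by chance

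*Protocol*

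**What the plan says.** Groups are defined by genotype only: "Each eligible participant will be assigned to a study group according to his CYP2C19 genotype" (Protocol 4.4). Section 4.2 admits men and women aged 18-65, with no quota or matching. In section 9.1 the 10 PMs and 30 NM-RM-UMs "subjects will be recruited and compared to each other at baseline", as validation of the features found in part 1. Section 9.2 names one univariate method for both kinds of contrast, a volcano plot to detect "significant changes in signal intensities before and after inhibition or induction as well as between PMs and NMs-RMs-UMs". Section 3.2 qualifies a feature as a CYP2C19 biomarker at a fold-change of at least 1.5 or at most 0.67, and that rule contains no p-value.

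On sex, section 2.3 states that "CYP2C19 activity might also be influenced by pregnancy, oral contraceptives and gender", and the eCRF list in section 8.1.1 contains "Demography: gender*, age". Neither variable appears in the description of the PM contrast or in the choice of the 30 comparators.

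**The concern.** In the session contrasts each volunteer is his or her own control, so a fixed sex difference in an ion cancels. Section 3.1 relies on this pairing when it dismisses bias from the session order. The pairing does not extend to the genotype contrast, which compares different people and has only 10 in one arm.

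For an ion whose level depends on sex, leaving sex out does two things. Sex variance is added to the error term, which makes a true genotype effect harder to see. A chance difference in the share of women between the groups also shifts the observed fold-change, and section 3.2 acts on the fold-change alone.

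The session step does not reliably screen out such ions, because the modulators are not specific: "Rifampicin acts as a strong inducer of CYP2C8, 2C9, 2C19 as well as 3A4/5". Section 2.2 says of the cytochromes P450 that "Most of them have endogenous functions such as biosynthesis of steroid hormones, prostaglandins and bile acids". Steroid-type ions are therefore a plausible exposed class, though the protocol does not show that they are one. At stake is which part 1 candidates are accepted or lost at the genotype step.

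**Working it through.** **The plan's own figure.** Section 9.1 uses a "two-sided paired samples t-test with a power" of 80%, alpha 0.05/5000 = 1e-5 and effect size 1.156. The exact noncentral-t calculation gives n = 30 (power 0.804; 0.768 at n = 29), so the stated 30 reproduces. It covers only the paired part. No power is stated for 10 versus 30.

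**Inputs.** From the protocol: n = 10 and 30; limits 1.5 and 0.67. Assumed, because the documents give none of them: half women, within-sex log SD s of 0.35, 0.6 or 0.9, sex ratio r of the ion, true PM effect 2-fold, two-sided 0.05 (section 9.2 applies the FDR adjustment only to the session contrasts).

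**Power.** If sex is ignored, the SD is S = sqrt(s² + 0.25·(ln r)²), with 38 df. With a sex term it is s, with 37 df. The noncentrality is ln 2 / (SD·sqrt(1/10 + 1/30)), and sqrt(1/10 + 1/30) = 0.365.

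Example with s = 0.6 and r = 3: S = sqrt(0.36 + 0.25·1.0986²) = 0.8135. Noncentrality is 0.693/(0.8135·0.365) = 2.33, giving power 62%. Adjusted, it is 0.693/(0.6·0.365) = 3.16, giving 87%.

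| Within-sex SD | 2-fold sex difference | 3-fold | 5-fold | Adjusted |
|---|---|---|---|---|
| 0.35 | 96% | 81% | 56% | about 100% |
| 0.6 | 76% | 62% | 45% | 87% |
| 0.9 | 48% | 42% | 34% | 54% |

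A separate simulation, with the genotype effect set at 1.156 within-sex SD, gave 0.79 unadjusted against 0.86 adjusted at a sex gap of 1 SD, and 0.58 against 0.86 at 2 SD. With no sex effect it gave 0.87 against 0.86, so an unneeded sex term costs about 1 point.

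**Null ions crossing the limits.** On the log scale the fold-change of an ion with no genotype effect has SD of about S·0.365. The chance of crossing is about 2·Φ(−ln 1.5/(S·0.365)), taking 0.67 as 1/1.5.

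- s = 0.6: for r = 3, 0.405/0.297 = 1.37, so 17%; for r = 5, 0.405/0.367 = 1.11, so 27%. Adjusted, 0.405/0.219 = 1.85, so 6.4%, or 7% by simulation once the cost of estimating the sex term is included.
- s = 0.35: for r = 3, 0.405/0.238 = 1.71, so 9%; for r = 5, 0.405/0.320 = 1.27, so 21%. Adjusted: 0.2%.
- s = 0.9: for r = 3, 0.405/0.385 = 1.05, so 29%; for r = 5, 0.405/0.441 = 0.92, so 36%. Adjusted: 22%.

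**Imbalance alone.** With 20 women among 40, a 7:3 or worse split among the PMs has probability 27%, and 8:2 or worse 6.5%. At 7:3 the shares differ by 0.70 − 13/30 = 0.267, and imbalance by itself reaches 1.5-fold only if r = 1.5^(1/0.267) = 4.6. At 8:2 the difference is 0.80 − 12/30 = 0.40, and r = 1.5^(1/0.40) = 2.8. Below those ratios, crossing needs noise as well.

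**Type I error.** In simulation the unadjusted t-test stays at about 5% for every sex gap tried.

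**The case against.** *Covariates belong in a statistical analysis plan.* They often do, and section 9.2 nowhere says that the test is unadjusted, so a bare omission would not be a finding. But the protocol itself fixes the contrast, the display and the qualification rule, and names gender as an influence. A better analysis of data it already collects is almost free.

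*A volcano plot also uses a p-value.* If an ion must both cross the limits and reach p < 0.05, the excess of false crossings at s = 0.6 nearly vanishes (5.0% against 4.5% adjusted). At s = 0.35 it does not (5% against 0.2%). Section 3.2 as written asks for the fold-change alone.

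*The false-positive route is filtered.* This stands. An ion must first change under fluvoxamine or rifampicin, so the crossing rates apply only to ions past that step. Section 2.9 adds correlation with the omeprazole ratio, recombinant enzymes and genotyped hepatocytes. Those checks can remove a false candidate, but they do not recover a true marker missed at the genotype step.

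*The inputs are assumed.* This also stands. Section 2.3 says that gender might influence enzyme activity; it gives no size and does not speak of ion levels.

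A reader might infer more than the documents support. That sex-dependent ions lose most of their power does not hold for 2- to 5-fold sex differences: no entry in the table loses more than half, and at s = 0.6 power falls to 30% only at about a 10-fold difference. That the unadjusted test gives too many small p-values is wrong, as shown above. No age effect is given or can be sized from the protocol, so age carries no weight here.

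**Conclusion.** The concern holds as a loss of precision in an unpaired 10 versus 30 contrast, combined with a qualification rule that has no p-value. For ions differing 2- to 5-fold by sex, ignoring sex costs about 11 to 42 power points at within-sex SD 0.6 (87% down to 76% and 45%). It costs about 4 to 44 points at SD 0.35 and 6 to 20 at SD 0.9. False crossings under the fold-change-only rule rise from 7% to 17-27% at SD 0.6, and from 0.2% to 9-21% at SD 0.35, for 3- to 5-fold sex differences. Ions that do not depend on sex are unaffected.

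The direction is certain. The size rests on the assumed SD, sex ratios, share of women and 2-fold PM effect. The paired session analyses and the sample size of 30 are not touched. This is a change the sponsor should make because it is cheap, not a flaw that invalidates the study.

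**What to change.** In section 9.2, analyse PM versus NM-RM-UM by a linear model on log intensity for each ion, with genotype group and sex as terms and age as an optional second covariate. Take both the fold-change and the p-value from the adjusted genotype coefficient, and apply the 1.5 and 0.67 limits of section 3.2 to that estimate.

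In section 4.4, add that the share of women among the NM-RM-UMs will be kept close to that of the PMs where recruitment timing allows. Table 1 gives 39.61% + 27.12% + 4.64% = 71.37% NM-RM-UMs against 2.39% PMs, about 30 to 1, so suitable comparators are plentiful. This is not strictly free, because the PM share becomes known only as the scarce PMs enrol and some extra screening may be needed. The adjusted model does not depend on it.

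Cost: one or two of 38 degrees of freedom, about 1 power point if sex has no effect, a sentence in each section, and no new data.
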